2.1.2 Phase 1b Clinical Study Results

The BPZE1 investigational liquid vaccine was safe in the higher doses and volumes used for nasal administration. Proportion of subjects having transiently BPZE1 colonized nasopharyngeal mucosa was not dose-related at 10^7 CFU or higher, but instead all dosage groups achieving 75% colonization rate or greater, and an overall combined colonization rate was observed for subjects from all randomized groups of over 80%. A dose response trend was observed, however, in the rate of colonization and clearance, with faster colonization rate and faster clearance rate being correlated with higher dosage. The serum antibody responses were strongly correlated to positive colonization, but there was no dose response. A small non-randomized group of subjects with

pre-existing high antibody titers for pertactin had a 33% rate of BPZE1 colonization after immunization with the 10^9 CFU dose.

There were no SAEs and any differences in AEs within randomized study groups, between placebo and the different dosages, were not detectable. The most frequent AEs were sneezing (n=55 episodes in 24 subjects), rhinorrhea (n=35 episodes in 22 subjects), nasal congestion (n=31 episodes in 19 subjects), cough (n=21 episodes in 16 subjects), and fatigue (n=21 episodes in 16 subjects). Efficacy results, included:

- *Colonization of mucosal surface:* The vaccine strain BPZE1 was isolated in a total of 29 randomized subjects, 10 in the 10^7 CFU dose group, 9 in the 10^8 CFU dose group, and 10 subjects in the 10^9 CFU dose group. Colonization was first detected on day 4-14 and lasted through day 11-28 after vaccination.
- *Immunogenicity:* Serologic responses (IgG and IgA) were measured to PT, PRN, FIM, and FHA and reported individually. In addition, responses were grouped by either:
 - ≥ 2 -fold rise in PT-specific IgG or IgA that was at least 4x greater than the minimum limit of detection (MLD) of the assay, or
 - ≥ 2 -fold rise in at least 2 antibodies targeting PRN, FIM, or FHA (IgG or IgA) that were at least 4x greater than the MLD

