4 STUDY DESIGN

This is a phase 2a, single center, randomized, partially blind, placebo controlled, clinical trial evaluating a single intranasal dose of either 10^7 CFU or 10^9 CFU of BPZE1 in healthy adults (18-49 years of age, inclusive). The study will evaluate a lyophilized formulation of the product, with the goal of testing for the optimal dose for subsequent clinical trials. Since it is anticipated that the VaxINator device will be the primary mechanism of delivery in subsequent clinical trials, the majority of volunteers will receive vaccine or placebo via VaxINator device. Five individuals will receive 10^9 CFU of BPZE1 by needleless tuberculin syringe in order to compare immunogenicity to previous Phase 1 clinical trials of BPZE1.

We anticipate that enrollment will require approximately 12 months, with each subject participating for 6 months. Fifty healthy adults, 18-49 years of age will be randomized to one of four treatment groups in a 3:3:3:1 ratio, as described in the table below. Safety will be assessed through an Independent Safety Monitor (ISM) and a Safety Monitoring Committee (SMC) described in [Section 9.6](#).

Table 2: Treatment Groups and Intranasal Vaccine to be Administered

| Group | N | Intranasal Vaccination | Device Used for Administration |
|-------|----|------------------------|--------------------------------|
| 1 | 15 | BPZE1 10^7 CFU | VaxINator |
| 2 | 15 | BPZE1 10^9 CFU | VaxINator |
| 3 | 15 | Placebo | VaxINator |
| 4 | 5 | BPZE1 10^9 CFU | Needleless Tuberculin Syringe |

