11.4.3 Immunogenicity Data

Summaries and analysis of immunogenicity data will be presented for the immunogenicity and PP populations by treatment group.

Immune responses in terms of toxin-specific serum IgG and IgA antibody titers (PT, FHA, PRN, FIM 2/3) will be summarized at each time point. Analyses will include the Geometric Mean Titers (GMTs) along with corresponding 95% confidence intervals and Geometric Mean Fold Rise (GMFR), as well as the proportion of subjects achieving seroconversion (defined as 2-fold increase over baseline of GMT) for each antigen (PT, FHA, PRN, and FIM 2/3) and the proportion of subjects that achieved seroconversion for ≥ 1 and ≥ 2 antigens (PT, FHA, PRN, and FIM 2/3).

Immune responses in terms of the ratio of toxin-specific (PT, FHA, PRN, FIM 2/3) nasal mucosal IgA antibody to total nasal mucosal IgA antibody will be summarized at each time point. Analyses will include the geometric mean titer ratios (GMTR) of antigen-specific IgA to total IgA and corresponding 95% confidence intervals, along with fold change of the GMTR from baseline. The proportion of subjects achieving seroconversion, defined as ≥ 2 -fold rise of the GMTR from baseline, to each antigen (PT, FHA, PRN, and FIM 2/3) will be reported as well as the proportion of subjects that achieve seroconversion by nasal aspirate ELISA to one or more antigens (PT, FHA, PRN, and FIM 2/3) at either or both of Day 29 and Day 181.

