3.2.2. Secondary Outcome Measures

Humoral Immune Response

- Geometric mean titers (GMTs) by serum IgG and IgA ELISA to PT, FHA, PRN, FIM 2/3 on Days 1, 15, 29, and 181
- Geometric mean fold rise (GMFR) by serum IgG and IgA ELISA to PT, FHA, PRN, FIM 2/3 on Days 15, 29 and 181 relative to baseline (Day 1)
- The proportion of subjects that achieve seroconversion (defined as ≥ 2 -fold rise from baseline) to individual pertussis antigens (PT, FHA, PRN, and FIM 2/3) by serum IgG or IgA ELISA at Days 15, 29, 181 or any time point relative to baseline (Day 1)
- Proportion of subjects achieving seroconversion (serum IgG or IgA ELISA) to one or more pertussis antigens at Days 15, 29, 181 or any time point, relative to baseline (Day 1)

- Proportion of subjects achieving seroconversion (serum IgG/IgA ELISA) to two or more pertussis antigens at Days 15, 29, 181 or any time point, relative to baseline (Day 1)

Mucosal Immune Response

- Geometric mean titer ratios (GMTRs) and ratio of antigen-specific IgA ELISA (PT-IgA, FHA-IgA, PRN-IgA, FIM-IgA) to total IgA by nasal aspirate at screening, and Days 29 and 181.
- Fold rise of the ratio of antigen-specific IgA (PT-IgA, FHA-IgA, PRN-IgA, FIM-IgA) to total IgA by nasal aspirate from the screening visit to Days 29 and 181
- The proportion of subjects that achieve seroconversion (defined as ≥ 2 -fold rise of the ratio from baseline) to individual pertussis antigens (PT, FHA, PRN, and FIM 2/3) by nasal aspirate IgA ELISA at Days 29 and 181 or any time point relative to baseline (screening)
- Proportion of subjects that achieve seroconversion (≥ 2 -fold rise of the ratio from baseline) to at least 1 antigen (PT, FHA, PRN, or FIM 2/3) by nasal aspirate IgA ELISA from the screening visit to Days 29 and/or 181.

Nasal Clearance

- Proportion of subjects with detectable B. pertussis from nasopharyngeal cultures at Day 29.
- For those who remain positive at Day 29, the subjects with detectable B. pertussis at Day 46 will also be evaluated and reported. Detection of B. pertussis in culture will be assumed to be due to study-product administration.

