3.3. Study Definitions and Derived Variables

New Onset Chronic Medical Conditions (NOCMCs) will be defined as new medical conditions, not present at the time of screening or enrollment, that require ongoing medical care and intervention.

Achievement of seroconversion based on humoral response will be defined as a ≥ 2 -fold rise from baseline. Achievement of seroconversion based on mucosal response will be defined as a ≥ 2 -fold rise the ratio of antigen-specific IgA ELISA (PT-IgA, FHA-IgA, PRN-IgA, FIM-IgA) to total IgA by nasal aspirate from baseline.

Medically Significant Wheezing will be defined as clinician (licensed to make medical diagnoses) documented wheezing on PE accompanied by any one or more of the following: Respiratory distress (tachypnea, retractions or dyspnea), Hypoxemia (O₂ saturation <95%), new prescription, or use of daily bronchodilator therapy (not on an “as needed” basis).

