8.1. Secondary Immunogenicity Analysis

Summaries and analysis of immunogenicity data will be presented for the immunogenicity and PP populations by treatment group.

Immune responses in terms of toxin-specific serum IgG and IgA antibody titers (PT, FHA, PRN, FIM 2/3) will be summarized at each time point. Analyses will include the Geometric Mean Titers (GMTs) along with corresponding 95% confidence intervals (Table 17, Table 18, Table 19, and Table 20) and Geometric Mean Fold Rise (GMFR) (Table 21, Table 22, Table 23, and Table 24), as well as the proportion of subjects achieving seroconversion (defined as 2-fold increase over baseline of GMT) for each antigen (PT, FHA, PRN, and FIM 2/3) and the proportion of subjects that achieved seroconversion for ≥ 1 (Table 25 and Table 26) and ≥ 2 (Table 27 and Table 28) antigens (PT, FHA, PRN, and FIM 2/3.) Rates of seroconversion will be compared using Barnard's exact test. Reverse cumulative distributions (RCD) curves will also be presented for PT, FHA, PRN, and FIM 2/3 antibody titers. Plots for each assay will be generated with four panels (pre-vaccination, Day 15, Day 29, and Day 181), and separate curves within each panel for each treatment group, as shown in Figure 3, Figure 4, Figure 5, and Figure 6. Individual immunogenicity response data will also be presented (Listing 7 and Listing 8.)

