Immune responses in terms of the ratio of toxin-specific (PT, FHA, PRN, FIM 2/3) nasal mucosal IgA antibody to total nasal mucosal IgA antibody will be summarized at each time point (Table 29 and Table 30.) Analyses will include the geometric mean titer ratios (GMTR) of antigen-specific IgA to total IgA and corresponding 95% confidence intervals, along with fold change of the GMTR from baseline. The proportion of subjects achieving seroconversion, defined as ≥ 2 -fold rise of the GMTR from baseline, to each antigen (PT, FHA, PRN, and FIM 2/3) will be reported (Table 29 and Table 30) as well as the proportion of subjects that achieve seroconversion by nasal aspirate ELISA to one or more (Table 31 and Table 32) antigens (PT, FHA, PRN, and FIM 2/3) at either or both of Day 29 and Day 181. Rates of seroconversion will be compared using Barnard's exact test. Reverse cumulative distributions (RCD) curves will also be presented for mucosal PT, FHA, PRN, and FIM 2/3 antibody titers. Plots for each assay will be generated with three panels (pre-vaccination, Day 15, Day 29, and Day 181), and separate curves within each panel for each treatment group, as shown in Figure 7 and Figure 8. Individual immunogenicity response data will also be presented (Listing 9.)

Subjects will be tested for *B. pertussis* colonization by culture at Day 29 and, if positive, again at Day 46. The proportion of subjects with positive *B. pertussis* culture will be reported for the PP population at each time point with corresponding 95% confidence intervals (Table 33.) Individual nasal colonization data will also be presented (Listing 13.)

No formal hypothesis testing is planned.

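### SAP 8.1 and Protocol 11.4.3 define a subject's seroconversion by a group statistic, and no table derives the Phase 1b response with which the syringe arm is meant to be compared

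*SAP*

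**What the plan says.** The two analysis sections use a group mean as the reference. SAP 8.1 has "seroconversion (defined as 2-fold increase over baseline of GMT" and Protocol 11.4.3 has "proportion of subjects achieving seroconversion (defined as 2-fold increase over baseline of GMT". For the nasal samples, SAP 8.1 counts subjects with a 2-"fold rise of the GMTR from baseline, to each antigen", and Protocol 11.4.3 agrees.

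Elsewhere the rule is per subject. SAP 3.2.2 begins "The proportion of subjects that achieve seroconversion (defined as" and continues with a rise of at least 2-fold from baseline; Protocol 3.2.2 matches it. SAP 3.3 begins "Achievement of seroconversion based on humoral response will be defined as a" and ends the same way. The footnotes to SAP Tables 21, 25, 29 and 31 count subjects by rise over the pre-dose value. Listings 7 to 9 show each subject's titre and fold rise.

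The composite endpoints count seroconversion "to one or more pertussis antigens at Days 15, 29, 181 or any time point", and likewise to two or more antigens.

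Protocol 2.1.2 reports a stricter grouped response for Phase 1b: a 2-fold rise in PT IgG or IgA reaching at least four times the MLD, or a 2-fold "rise in at least 2 antibodies targeting PRN, FIM, or FHA (IgG or IgA) that were at least 4x greater than the MLD". Protocol 4 includes the five-subject syringe arm "in order to compare immunogenicity to previous Phase 1 clinical trials of BPZE1". Protocol 11.4 splits the 10^9 CFU results by device for that purpose, while the opening of Protocol 11 calls the comparison historical and informal.

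**The concern.** A programmer looks to the analysis section for the derivation, and there the reference value is a statistic that no individual subject has. If the derivation followed it, subjects would be classified by where they stand relative to their group rather than by whether they rose.

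The second issue is the bridge to Phase 1. The Phase 1b rates quoted in Protocol 2.1.2 (above 92% at 10^7 CFU and 100% at 10^9 CFU for at least one antibody; no placebo subject with two seropositive antibodies or with PT) all carry the floor of four times the MLD. The planned tables do not. A reader who sets the new rates beside the old ones would be comparing different response definitions. Protocol 11.4 says the results inform the Phase 2b dose, and the Preliminary Report may be released for planning later trials.

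**Working it through.** **Step 1. The plan's own figure.** Table 4 gives detectable seroconversion rates for 15 against 15 (two-sided Fisher's exact test, alpha 0.05, 80% power). Enumerating all 16 x 16 outcomes, the power at the five printed pairs is 0.805, 0.792, 0.805, 0.793 and 0.805. Table 4 reproduces. It covers placebo rates of 0 to 0.20 and is stated for individual antigens.

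**Step 2. The definitions side by side.**

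| Place | Reference for the 2-fold rise | Level |
|---|---|---|
| Protocol 3.2.2, SAP 3.2.2 | baseline: Day 1 for serum, screening ratio for nasal samples | subject |
| SAP 3.3 | baseline | subject |
| Footnotes to SAP Tables 21, 25, 29, 31 | pre-dose value | subject |
| SAP Listings 7 to 9 | fold rise shown per subject | subject |
| Protocol 11.4.3, SAP 8.1 (serum) | GMT | group |
| Protocol 11.4.3, SAP 8.1 (mucosal) | GMTR | group |

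**Step 3. What the literal rule would do.** The documents give no titre SD, so 0.2 to 0.6 log10 is an assumption. With normal log titres, an unchanged titre is at least twice the group baseline GMT with probability 1 - Phi(log10(2)/SD), where log10(2) = 0.301. A true 3-fold riser is missed with probability Phi((log10(2) - log10(3))/SD).

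| SD (log10) | Unchanged titre counted | Expected of 15 | 3-fold riser missed |
|---|---|---|---|
| 0.2 | 6.6% | 1.0 | 18.9% |
| 0.3 | 15.8% | 2.4 | 27.9% |
| 0.4 | 22.6% | 3.4 | 33.0% |
| 0.5 | 27.4% | 4.1 | 36.2% |
| 0.6 | 30.8% | 4.6 | 38.5% |

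With the subject's own baseline, an unchanged titre has a ratio of 1 and is never counted.

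**Step 4. The Phase 1b response against the planned composites.**

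| | Phase 1b grouped response | SAP Tables 25 to 28 |
|---|---|---|
| Rise | at least 2-fold | at least 2-fold |
| Floor | at least 4 x MLD | none |
| Combination | PT alone, or at least 2 among PRN, FIM, FHA | at least 1, or at least 2, of all four antigens |

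Neither composite is the Phase 1b response. A subject who rises on PT alone could respond in Phase 1b but fails the two-antigen composite. A subject who rises on FHA alone fails in Phase 1b but passes the one-antigen composite. At the same visits, the one-antigen rate is an upper bound for the Phase 1b rate. Without a floor, the two-antigen rate would be a lower bound; with the floor, even that is lost.

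Listings 7 and 8 have no MLD field, and SAP Appendix 3 leaves all listings out of the Preliminary Report.

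**Step 5. Chance doublings under the plain subject-level rule.** No assay CV is given; 20% to 30% is an assumption, as is independence across the 8 analytes (4 antigens, IgG and IgA). With s = sqrt(ln(1 + CV^2)), one comparison doubles by error alone with probability p = 1 - Phi(ln 2/(s x sqrt 2)).

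- CV 20%: s = 0.198, p = 1 - Phi(2.475) = 0.0067.
- CV 30%: s = 0.294, p = 1 - Phi(1.669) = 0.0475.

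For one antigen by either isotype at one visit the chance is 1 - (1 - p)^2. Across three visits, simulation with the shared baseline gives 1.75% and 11.2% per analyte, so one antigen at any visit is 1 - (1 - 0.0175)^2 and 1 - (1 - 0.1121)^2. The composites come from the same simulation.

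| CV | One antigen, one visit | One antigen, any visit | At least 1 antigen, Day 29 | At least 1, any visit | At least 2, any visit |
|---|---|---|---|---|---|
| 20% | 1.3% | 3.5% | 5.1% | 13.3% | 0.7% |
| 30% | 9.3% | 21.2% | 32.1% | 61.6% | 20.0% |

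The individual-antigen rates lie essentially within Table 4's placebo range. The one-antigen composite can leave it. At a placebo rate of 0.32, BPZE1 needs 0.87 for 80% power; at 0.62, 80% power cannot be reached with 15 per arm.

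**The case against.** **The group-mean wording is not operative.** The endpoint section, SAP 3.3, the table footnotes and the listings all use the subject's own rise, so a programmer working from the shells would derive the right ratio. This largely stands. A reader might infer from SAP 8.1 that unchanged titres will be counted, but the documents do not support that. The 7% to 31% describes a rule that the shells contradict. What remains is a contradiction in the section that is supposed to settle the derivation.

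**The Phase 1 comparison is informal and possible anyway.** A reader might infer that comparison with Phase 1 is impossible. It is not: GMTs and GMFRs by device need no floor, and individual titres are listed, so the Phase 1b rule could be applied later if the MLD is known. Formulation, country and possibly laboratory also differ, and five subjects say little: if all five responded, the lower exact 95% limit would be 0.025^(1/5) = 0.478. All of this stands. It does not justify presenting a different response definition when the matching one is easy to derive, nor does a later derivation help readers of the Preliminary Report.

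**The noise figures are not the effect of the missing floor.** This stands. Treating the 4 x 2 x 3 = 24 comparisons as independent gives 15% to 69% (1 - 0.9933^24 and 1 - 0.9525^24), which a reader might quote as the cost of dropping the floor. It ignores the shared baseline, which lowers it to about 13% to 62%. More importantly, a floor removes only doublings that end below four times the MLD. Without the MLD and the titre distribution, the rate after a floor cannot be computed. Positive correlation across analytes would lower all these figures, and the concurrent placebo arm will show the actual rate.

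**Putting the floor into the main definition would replace a prespecified endpoint.** This also stands, and the change is not recommended.

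**Conclusion.** Two points hold, and both rest on the text alone. SAP 8.1 and Protocol 11.4.3 state a group-level reference for a subject-level outcome and contradict the endpoint definition; this is most likely a drafting error and should be corrected. The Phase 1b response is not derived in any table, so response rates are not like for like with Phase 1b as planned, in floor and in antigen combination, while GMTs and GMFRs remain informally comparable.

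The sizes are conditional. The literal-rule figures depend on an assumed titre SD and apply only if the shells are overridden. The 13% to 62% for a chance doubling on any antigen at any visit depends on an assumed CV of 20% to 30% and independent errors, and only its low-titre part would go with a floor. Table 4 is correct for what it covers. These are secondary, descriptive endpoints, so the correction is worth making because it is cheap, not because the trial's conclusions are in danger.

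**What to change.** 1. In Protocol 11.4.3 and SAP 8.1, replace the references to the GMT and the GMTR. Serum: the subject's post-vaccination titre divided by that subject's own Day 1 titre is at least 2. Mucosal: the subject's ratio of antigen-specific to total IgA divided by that subject's own screening ratio is at least 2. Bring the footnotes of Tables 29 to 32 into line, since they refer to antibody and a pre-dose value rather than to the screening ratio.
2. Keep the plain 2-fold rise as the prespecified endpoint.
3. Add the Phase 1b responder definition as a supplementary row alongside Tables 25 to 28, for all four arms, and include it in the Preliminary Report. State the MLD for each assay and the value assigned to results below it, and say whether IgG and IgA to the same antigen count as one antibody or two.

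The cost is a wording change in two sections, one derived variable and a few extra table rows. The price for the reader is a second response rate, which must be labelled as supplementary so that it does not compete with the endpoint.

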9. SAFETY EVALUATION

All summaries and analysis of safety data will be presented for the Safety Analysis Population. Safety summaries will be presented overall and by treatment group.

Listings will be sorted by treatment group, subject ID, parameter (if applicable), and visit.

Continuous variables will be summarized using the following descriptive statistics: n (non-missing sample size), mean, standard deviation, median, maximum and minimum. All categorical measures will be summarized by the frequency and percentages (based on the non-missing sample size) of observed levels. The denominator for the percentages may be based on the number of non-missing observations for an assessment or based on the number of subjects in a population. This will be described for each table.

9.1. Demographic and Other Baseline Characteristics

Summaries of age, sex, ethnicity, and race will be presented by treatment group and overall ([Table 14](#) and [Table 15](#).) Ethnicity is categorized as Hispanic or Latino, or not Hispanic and not Latino. In accordance with NIH reporting policy, subjects may self-designate as belonging to more than one race or may refuse to identify a race, the latter reflected in the CRF as “No” to each racial option.

Individual subject listings ([Appendix 3](#)) will be presented for all demographics ([Listing 5](#);) pre-existing medical conditions ([Listing 6](#);) vital signs and oral temperature ([Listing 16](#);) and concomitant medications ([Listing 18](#).)

9.1.1. Prior and Concurrent Medical Conditions

All current illnesses and pre-existing medical conditions will be MedDRA® coded using MedDRA dictionary version 21.0 or higher. Summaries of subjects’ pre-existing medical conditions will be presented by treatment group ([Table 16](#).) Individual subject listings will be presented for all medical conditions ([Listing 6](#).)

9.1.2. Prior and Concomitant Medications

During screening, medications and vaccines used up to 30 days prior will be solicited. Any medications used within 30 days prior to signing the informed consent form through 28 days after study vaccination (or early termination if prior to 28 days after study vaccination) will be recorded in the eCRFs. In addition, receipt of non-study vaccines will be solicited through approximately 28 days after study vaccination and recorded in the eCRFs.

Summaries of medications that were started prior to dosing and continuing at the time of dosing will be presented by WHO Drug Terms 2 and 3 and treatment group ([Table 80](#).)

Individual subject listings will be presented for all concomitant medications ([Listing 18](#).)

